4.5.2 Laboratory Data

Summaries of laboratory data collected from baseline onward will include:

- Incidence of laboratory toxicities by NCI CTCAE toxicity version 4.03 grade. Separate summaries will be provided by time point, for the minimum post-baseline value, and for the maximum post-baseline value.
- Incidence of clinically significant toxicities by NCI CTCAE toxicity version 4.03. A clinically significant laboratory toxicity is defined as a toxicity with NCI grade < 3 at baseline that increased in severity to NCI grade ≥ 3 . Subjects with multiple occurrences of the same toxicity are counted only once.
- Shifts from baseline. The following shifts will be computed: a) Shifts from baseline to minimum post-baseline value, b) Shifts from baseline to maximum post-baseline value, c) Shifts from baseline to last post-baseline value or end of treatment, and d) Shifts from baseline to worst post-baseline value. Laboratory values will be categorized as Normal, High, or Low based on the normal reference range.
- Summary statistics (mean, median, standard deviation, minimum, maximum) for laboratory values and their change from baseline by time point.

4.5.3 Vital Signs

Vital sign change from baseline data (blood pressure, heart rate and body temperature), will be summarized descriptively by time point.

Data collected pre- and post-infusion will be summarized for each of the 3 infusions. Summaries of change values will be included in these summaries where change values will be calculated as post-infusion – pre-infusion.

A summary of clinically significant abnormal vital signs at the post-infusion visit and the shift table from pre-infusion visit will be provided for each of the 3 infusions. Clinically significant abnormal vital signs are defined as:

		Low	High	Comments
Blood Pressure:	Systolic (mm Hg)	< 90	≥ 140	High corresponds to NCI CTCAE Grade 2 hypertension.
	Diastolic (mm Hg)	< 40	≥ 90	
Heart Rate (bpm)		< 60	> 100	NCI CTCAE defines sinus brady- and tachycardia using these cut-offs (in presence of dysrhythmia)
Respiration (bpm)		< 10	> 28	
Temperature ($^{\circ}$ F/ $^{\circ}$ C)		$\leq 95.0/35.0$	$\geq 100.4/38.0$	High corresponds to NCI CTCAE Grade 1 fever. Low corresponds to NCI CTCAE Grade 1 hypothermia.

4.6 Other Data

4.6.1 Demographic and Baseline Characteristics

Demographic information and baseline disease information and characteristics will be summarized with descriptive statistics by treatment arm and overall for all analysis populations. The Wilcoxon test will be used to compare the treatment arms for continuous variables and Fisher's exact test will be used to compare the treatment arms for categorical variables.

4.6.2 Disposition

Subject disposition will be summarized by treatment group for the randomized population. This summary will include, but will not be limited to, the following:

- Number of subjects randomized
- Number of subjects who had at least one leukapheresis
- Number of subjects receiving at least one infusion of sipuleucel-T
- Number of subjects receiving Enzalutamide
- Number of subjects who prematurely discontinued each study treatment
- Reason(s) for premature discontinuation of each study treatment

- Number of subjects who prematurely discontinued the study (i.e., refused further study evaluations [with the possible exception of survival status])
- Reason(s) for premature discontinuation from the study
- Number of subjects who died
- Cause of death summary
- Number of subjects in the immune response, safety analysis, and efficacy analysis sets

In addition, the number of subjects screened for the trial will be summarized.

4.6.3 Concomitant Medications and Procedures

Concomitant medications and procedures will be presented in data listings by treatment group based on coded terms using the most current version at the time of analysis of the World Health Organization dictionary, “WHODRUG”. All subjects randomized will be included. Summary tables by treatment arm will be provided with separate tables for medications and procedures started prior to the day of randomization and medications and procedures started on or after the day of randomization.

4.6.4 Baseline Smoking History and Cerebrovascular Event Risk Factors

Baseline smoking history regarding cigarette smoking status and cigarette smoking pack years will be summarized descriptively by treatment group. Baseline cerebrovascular event risk factors will be summarized.

4.6.5 Baseline Medical History

Baseline medical history will be listed.

4.6.6 ECOG Performance Status

ECOG performance status will be summarized descriptively by treatment group by time point. In addition, the last ECOG collected will be compared to the baseline ECOG for each subject to determine the percentage of subjects whose ECOG score improved (ECOG score lower compared to baseline), stayed the same, or worsened (ECOG score higher compared to baseline). Shifts in ECOG from baseline to post-baseline at each visit and worst post-baseline ECOG will be presented.

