#### **8.4.3      Exploratory Endpoint(s)**

The time to next anticancer intervention is defined as the time from randomization to the first anticancer intervention. Those subjects without an anticancer intervention will be censored at their last follow-up assessment when anticancer therapy information is collected.

The time to first opioid use for cancer-related pain is defined as the time from randomization to the first use of an opioid for cancer-related pain. Those subjects without a record of opioid use for cancer-related pain will be censored at their last follow-up assessment when opioid use for cancer-related pain is collected.

The time to first ECOG performance status decline (i.e., increase in numerical value of ECOG performance status) is defined as the time from randomization to the first decline in ECOG performance status by 1 point or more. Those subjects without an ECOG performance status decline will be censored at their last follow-up assessment for ECOG performance status.

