its 2-sided, 95% CI, using the sequential arm as the denominator will be provided. The percentage of subjects free of PSA progression with an associated 95% CI at landmark time points such as 6 and 12 months will be provided by treatment arm as well as pooled over treatment arms using the Kaplan-Meier method.

Overall survival, time to next anticancer intervention, time to first chemotherapy, time to first cancer-related opioid use, and time to first ECOG performance status decline will be analyzed in a similar manner as described for time to PSA progression.

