2.3 Exploratory Study Objectives

- To evaluate time to next anticancer intervention.
- To evaluate time to first cancer-related opioid use.
- To evaluate time to Eastern Cooperative Oncology Group (ECOG) performance status decline.

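### The SAP keeps time to ECOG decline as an exploratory objective but plans only descriptive ECOG summaries, so timing, censoring and the between-arm hazard ratio are not estimated

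*SAP*

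**What the plan says.** **Protocol.** Section 8.4.3 gives the exploratory endpoint as the "time from randomization to the first decline in ECOG performance status by 1 point or more". It also gives a censoring rule: "Those subjects without an ECOG performance status decline will be censored at their last follow-up assessment for ECOG performance status". Section 8.5.3 states the method: "time to first ECOG performance status decline will be analyzed in a similar manner as described for time to PSA progression". For PSA progression, that means a Cox model with treatment, log baseline PSA and log baseline LDH, a hazard ratio with 95% CI (sequential arm as denominator), and Kaplan-Meier percentages at landmark times.

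**SAP.** Section 2.3 keeps the objective: "To evaluate time to Eastern Cooperative Oncology Group (ECOG) performance status decline". Section 4.6.6 then plans four outputs:
- by-visit summaries ("ECOG performance status will be summarized descriptively by treatment group by time point");
- last against baseline ("the last ECOG collected will be compared to the baseline ECOG for each subject"), classed as improved, same or worsened;
- shifts from baseline at each visit;
- worst post-baseline ECOG.

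Tables 14.2.22 to 14.2.24 match these. SAP 4.6.9 gives time-to-event analyses for next anticancer intervention, first chemotherapy and first cancer-related opioid use. It does not mention ECOG. The proposed figures include time-to-event plots for survival, anticancer intervention, chemotherapy and PSA progression, and none for ECOG decline. The SAP does not say that the ECOG analysis was withdrawn.

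**The concern.** Of the three exploratory objectives in SAP 2.3, ECOG decline is the only one with no time-to-event analysis in the SAP. Followed as written, the SAP answers a question about time with counts and percentages.

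Two things are at stake. First, the report would contain no hazard ratio, Kaplan-Meier estimate or censoring for an objective that it still lists. Second, a reader would compare the arms on crude proportions. That comparison needs similar ECOG follow-up in both arms, and the treatment schedule makes follow-up unequal. An analyst who adds the analysis later would also have to choose a censoring date with the data in hand, because the protocol's rule for this endpoint and the SAP's general rule differ.

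**Working it through.** No sample size, event count or power is stated for ECOG decline, so there is no figure of the plan's own to reproduce. The check is a comparison of the texts, followed by a calculation of follow-up length.

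**1. What the SAP summaries recover.** A man has a first rise of 1 point or more exactly when his worst post-baseline ECOG is above baseline. Table 14.2.24 therefore gives the crude proportion with the protocol's event. It does not give when the event happened or how long men without it were observed. The last-value table can only give a proportion equal to or below the worst-value one, since a man who is worse at the last visit has worsened at some point.

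**2. Timing of the post-treatment ECOG, for men who complete treatment.** Inputs:
- Concurrent arm: enzalutamide starts 2 weeks before the first leukapheresis and runs 52 weeks (Protocol 3.1).
- Sequential arm: enzalutamide starts about 10 weeks after the first infusion and runs 52 weeks (Protocol 3.1).
- Infusion comes about 3 days after leukapheresis, and the post-treatment visit 30 to 37 days after the last treatment (Protocol Table 1).
- Assumption: the delay d from randomization to the first study procedure (first enzalutamide dose or first leukapheresis) is the same in both arms.

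| | Concurrent | Sequential |
|---|---|---|
| Weeks from randomization | d + 52 + (30 to 37)/7 | d + 3/7 + 10 + 52 + (30 to 37)/7 |
| Result | d + 56.3 to 57.3 | d + 66.7 to 67.7 |

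The gap is 10 + 3/7 = 10.4 weeks. Counted from the first infusion, the visits fall near week 54 (52 - 2 - 3/7 + 30/7 = 53.9) and week 66 to 67 (62 + 30/7 = 66.3; 62 + 37/7 = 67.3).

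**3. What that gap does to a crude proportion.** Assume the same constant hazard in both arms, so that there is no treatment effect, with 30% decline at 12 months (52.18 weeks). The documents give no ECOG decline rate.
- Hazard = -ln(0.70)/52.18 = 0.00684 per week.
- Proportion ever worsened by week t = 1 - exp(-0.00684 t). Take d = 0.
- Concurrent, t = 56.3 to 57.3: 31.9% to 32.4%.
- Sequential, t = 66.7 to 67.7: 36.6% to 37.1%.

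That is about 32% against 37% with a true hazard ratio of 1. At an assumed 12-month rate of 20%, the same steps give about 21% against 25%. At 40% they give about 42% to 43% against 48%. The calculation treats decline as observed continuously and stops at the post-treatment visit.

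**4. Later ECOG values.** Protocol Table 1 continues ECOG in long-term follow-up while a man stays on enzalutamide, then takes one final value. Later values shift both arms alike if use of enzalutamide after study supply is similar. The summaries contain nothing that checks this.

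**5. Censoring rules side by side.** Protocol 8.4.3 censors a man without decline at his last ECOG assessment. SAP 3.4 censors subjects who leave the study early without the event at their last known alive date. ECOG is not collected throughout survival follow-up, so the SAP 3.4 date can credit a man with decline-free time during which ECOG was not observed.

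**6. Precision of the hazard ratio.** With 25 and 27 men (SAP 3.1) and the proportions in step 3, expected events are 25 x 0.32 + 27 x 0.37 = 18. The standard error of the log hazard ratio is about 2/sqrt(18) = 0.47, so the 95% limits lie a factor exp(1.96 x 0.47) = 2.5 either side of the estimate.

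**The case against.** The strongest reply is that little is lost. The endpoint is exploratory. Enrolment was cut to 52, and SAP section 4 makes all analyses descriptive or exploratory. SAP section 5 leaves table content to a separate report plan and says final outputs may differ from the list. The worst-value table already shows how many men ever worsened. A hazard ratio with limits 2.5-fold either side would change no trial conclusion. All of this stands, and it sets the severity. It does not remove the mismatch: latitude over outputs neither specifies nor withdraws an analysis, and the worst-value table carries the unequal follow-up of step 2.

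A reader might infer more than the documents support:
- **That last against baseline is the SAP's sole ECOG comparison.** It is not; SAP 4.6.6 and Table 14.2.24 also give shifts and the worst value.
- **That the SAP reports a far smaller quantity than the protocol's.** For the last-value table, the shortfall depends on how often men recover, which the documents do not give. With no recovery it is zero, and it does not apply to the worst-value table.
- **That death must count as a decline because Appendix 1 lists it as grade 5.** Protocol 8.4.3 censors men without a decline at their last ECOG assessment, and nothing there scores death as an ECOG assessment. A decline-or-death composite would be a new endpoint.
- **That the handling of death would outweigh any difference between the arms.** The documents give no arm effect on ECOG to compare it with.

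**Conclusion.** The point holds in a limited form. The SAP retains a time-to-event objective and supplies descriptive summaries in place of the protocol's Cox and Kaplan-Meier analysis, without saying that the analysis was dropped. This follows from the texts alone.

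The crude last-value and worst-value proportions are not a fair substitute between arms. For treatment completers, the timing gap of about 10 weeks follows from the protocol's schedule, given equal start delays. The resulting difference of about 5 percentage points is an illustration: it rests on an assumed common constant hazard with 30% decline at 12 months, and runs from about 3 to 6 points for 20% to 40%. It says nothing about men who stop early, and it predicts no direction for the actual result.

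Severity is low, because the endpoint is exploratory and any hazard ratio would be imprecise.

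**What to change.** In SAP 4.6.6:

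1. Restore the protocol endpoint: time from randomization to the first ECOG rise of 1 point or more, with men without a decline censored at their last ECOG assessment (Protocol 8.4.3).
2. Analyse it as in Protocol 8.5.3: Cox model with treatment, log baseline PSA and log baseline LDH, hazard ratio with 95% CI (sequential arm as denominator), and Kaplan-Meier estimates by arm.
3. State that for this endpoint the Protocol 8.4.3 censoring rule takes precedence over the last-known-alive rule in SAP 3.4.
4. Add one table and one Kaplan-Meier figure to SAP section 5.
5. Label the last-against-baseline and shift tables, including worst post-baseline ECOG, as descriptive.

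The cost is a paragraph of SAP wording, one table and one figure, all from data already collected.

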4.6.7 Protocol Deviation and Eligibility Deviation

Protocol deviations will be summarized in a table and all the protocol deviations including significant protocol deviations will be presented in a listing. Eligibility deviations will be summarized in a separate table.

4.6.8 Study Treatment Administration

To evaluate the sipuleucel-T infusion success and failure rate over the course of the study, the following information will be summarized:

- a) Number of subjects who received a total of 0, 1, 2, or 3 infusions
- b) Number of subjects undergoing leukapheresis for infusions 1, 2, and 3
- d) Number of subjects undergoing leukapheresis more than once for infusions 1, 2, and 3
- e) Number of subjects failing to receive three infusions due to insufficient TNC count and/or CD54 upregulation
- f) Elapsed time between infusions
- g) Elapsed time between randomization and infusion 1

Items a) through e) will be summarized by their frequency distribution and by treatment group. Items f) and g) will be summarized with descriptive statistics (mean, median, standard deviation, minimum, and maximum) by treatment group.

The duration of treatment with enzalutamide will be summarized descriptively by randomized treatment groups. The reasons for stopping enzalutamide will be summarized descriptively by randomized treatment groups.

4.6.9 Anti-Cancer Interventions and Cancer-Related Opioid Use

All anticancer therapies received prior to screening and through the end of the LTFU phase were collected. Anticancer therapies included, but were not limited to, radiation, chemotherapy, hormone therapy, investigational cancer therapies, all other systemic therapies, and surgery. Each subject's first cancer-related opioid use will be collected and is defined as an opioid used for cancer-related pain that is of at least 2 consecutive days in duration.

The time to next anticancer intervention will be summarized by treatment group and is defined as the time from randomization to the first anticancer intervention as described above. Subjects who do not received any anti-cancer therapies will be censored at the last available contact date. A Cox regression model with treatment arm as the independent variable and stratified by screening PSA levels and screening lactate dehydrogenase will be used to compare the treatment arms with respect to time to first anti-cancer therapy. A similar summary will be produced for the time to first chemotherapy post randomization and time to first cancer-related opioid use.

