3.4 Data Rules

- *Study Day* = [(visit date) – (date of first infusion [Day 0])]. If the infusion does not occur, Day 0 will be the date of the first leukapheresis, unless it fails, in which case, Day 0 will be the date of registration.
- *Baseline*: baseline is defined as the value closest to but prior to the randomization data.
- *Change from baseline*: change from baseline is the post-baseline value minus the baseline value.
- *Percent change from baseline*: percent change from baseline is calculated as $100 \times (\text{post-baseline value} - \text{baseline value}) / \text{baseline value}$. If the baseline or post-baseline value is missing, then the change from baseline and percent change are set to missing. If the baseline value is zero and the post-baseline is non-zero, then the percent change from baseline is set to missing. If the baseline value is zero and the post-baseline value is also 0, then the percent change from baseline is set to 0.
- *Partial Dates*: Dates missing the day, month and year and the day and month will not be imputed. However, if the month and year are present, the day may be set to the 15th of the month or to a date consistent with a more conservative approach to the analysis of the data point.
- *Missing event or censor date*: If the date of an event or the date of censoring is missing for a time-to-event variable, the last known study date will be used. Subjects who prematurely discontinue from the study before having the event will be censored at their last known alive date.

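### Time to next anticancer intervention, first chemotherapy and first opioid use censor men who die event-free, so one minus Kaplan-Meier overstates the share who have the event

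*SAP*

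**What the plan says.** **Censoring.** SAP 4.6.9 states the rule for time to next anticancer intervention: "Subjects who do not received any anti-cancer therapies will be censored at the last available contact date". It then adds: "A similar summary will be produced for the time to first chemotherapy post randomization and time to first cancer-related opioid use". Protocol 8.4.3 has matching rules for two of the endpoints. For next intervention: "Those subjects without an anticancer intervention will be censored at their last follow-up assessment when anticancer therapy information is collected". For opioids: "Those subjects without a record of opioid use for cancer-related pain will be censored at their last follow-up assessment", meaning the last assessment at which opioid use is collected. The general rule in SAP 3.4 is: "Subjects who prematurely discontinue from the study before having the event will be censored at their last known alive date". None of these rules mentions death, and neither document mentions competing risks or cumulative incidence.

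**Estimation.** Protocol 8.5.3 lists "time to next anticancer intervention, time to first chemotherapy, time to first cancer-related opioid use" among the endpoints that "will be analyzed in a similar manner as described for time to PSA progression". The PSA-progression method is a Cox model plus the percentage event-free at landmarks such as 6 and 12 months, which "will be provided by treatment arm as well as pooled over treatment arms using the Kaplan-Meier method". SAP 4.6.9 itself names only a summary by arm and a stratified Cox model. The SAP's list of proposed figures has time-to-event plots for first anticancer intervention (Figure 11) and first chemotherapy (Figure 12). It has none for opioid use, which gets a summary table (14.2.20.1).

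**Horizon.** SAP 4.7.2 places the final analysis at about 3 years of survival follow-up for every subject.

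**The concern.** A man who has died cannot start chemotherapy, another therapy or an opioid. Kaplan-Meier with death as censoring assumes that he could still do so, at the same rate as the men who remain under observation. One minus Kaplan-Meier then describes a population in which nobody dies before the event. It is not the share of enrolled men who have the event, which is how a clinical reader will take a reported percentage or a plotted curve.

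Death is frequent here. Protocol 1.1.1 calls metastatic castrate-resistant disease lethal, with median survival of 12.2 to 27.2 months in recent Phase 3 studies. SAP Section 4 makes every analysis descriptive or exploratory, so for these endpoints the percentages and curves are the main output. What is at stake is an overstated account of how many men go on to chemotherapy or opioids. A test decision is not at stake.

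**Working it through.** **No plan figure to reproduce.** The documents give no event rate, event count or sample size for these endpoints. Their power statements (43 and 25 per arm) concern only the primary immune endpoint.

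**Inputs**

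- Median survival 25.8 months: Protocol 1.1.2, sipuleucel-T group of the pivotal trial.
- Times: 6 and 12 months (Protocol 8.5.3), and 36 months as the approximate end of follow-up (SAP 4.7.2). Neither document names 36 months as a landmark for these endpoints.
- Assumed: constant hazards; event median *m* from 6 to 36 months; hazard of death before the event equal to *k* times the overall death hazard, with *k* = 0.25, 0.5 or 1.0.

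**How common death is.** By 36 months, 1 − 2^(−36/25.8) = 62% of men would have died. The range is 60% to 87% for median survival of 27.2 down to 12.2 months.

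**Formulas.** Event hazard a = ln 2/m. Death-before-event hazard b = k × ln 2/25.8.

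- One minus Kaplan-Meier: 1 − exp(−at)
- Cumulative incidence: a/(a+b) × [1 − exp(−(a+b)t)]

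**Worked case, m = 24, k = 0.5.** a = 0.02888, b = 0.01343, a+b = 0.04231, a/(a+b) = 0.6825.

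- 12 months: one minus Kaplan-Meier = 29.3%; cumulative incidence = 0.6825 × (1 − 0.6018) = 27.2%; gap 2.1 points.
- 36 months: 64.6% against 0.6825 × (1 − 0.2180) = 53.4%; gap 11.3 points before rounding.

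**Overstatement in percentage points, for m = 6, 12, 24, 36 months**

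| Time | k = 0.25 | k = 0.5 | k = 1.0 |
|---|---|---|---|
| 6 months | 0.9, 0.5, 0.3, 0.2 | 1.7, 1.1, 0.6, 0.4 | 3.4, 2.1, 1.2, 0.8 |
| 12 months | 2.3, 1.7, 1.1, 0.8 | 4.5, 3.4, 2.1, 1.5 | 8.6, 6.5, 4.0, 2.9 |
| 36 months | 5.1, 6.7, 6.0, 5.0 | 9.7, 12.6, 11.3, 9.3 | 17.8, 22.5, 19.8, 16.2 |

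**Simulation check.** With 52 subjects (the number enrolled, SAP 3.1), 4,000 runs and m = 24, the mean 36-month estimates from Kaplan-Meier and Aalen-Johansen were 64.8% and 53.5% at k = 0.5, and 64.7% and 44.9% at k = 1.0. These agree with the formulas.

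**Sensitivity to survival.** At k = 1.0, varying median survival over 12.2 to 27.2 months gives a 36-month gap of 16 to 38 points.

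**Not included.** SAP Section 4 allows efficacy observations to be censored at the next anticancer intervention. If applied to chemotherapy or opioid use, that would be a further source of informative censoring.

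**The case against.** **The SAP section does not name Kaplan-Meier.** It plans a summary and a Cox model, and Figures 11 and 12 are titles marked as subject to change. This is true. Kaplan-Meier reaches these endpoints through Protocol 8.5.3, but that section names all three and nothing in the SAP withdraws it.

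**The named landmarks are early.** A reader might infer an overstatement of 16 to 22 points. That figure needs a 36-month reading, which is not a stated landmark, and k = 1.0, under which men who have not needed further therapy or opioids die at the full overall rate. These events often precede death, so a smaller k is plausible. At 6 and 12 months, with k = 1.0 and event medians of 12 to 36 months, the gap is only 0.8 to 2.1 and 2.9 to 6.5 points. This part of the objection stands and sets the size stated in the verdict.

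**The endpoints differ.** Anticancer intervention includes hormone therapy, radiation and surgery, so few men may die without any. One figure should not be applied to all three endpoints.

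**Other outputs help.** First-event tables, overall survival by arm and causes of death are already planned. They let a careful reader judge how common death is, but they do not give a cumulative incidence.

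**Precision is low.** With 25 and 27 men, a proportion near 50% has a 95% half-width of 1.96 × √(0.25/25) = 19.6 or 1.96 × √(0.25/27) = 18.9 points, even without censoring. That exceeds the bias at 12 months. Still, the bias always has the same sign and is avoidable.

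**Conclusion.** The point holds as a low-consequence improvement. The direction is certain once any man dies event-free and later events are observed. The size rests on assumed rates: exponential times, 25.8-month median survival, event medians of 6 to 36 months and k from 0.25 to 1.0. Under these, one minus Kaplan-Meier is too high by about 1 to 9 points at 12 months (0.8 to 8.6), and by 5 to 23 points if the curves are read at 36 months. The effect is probably smallest for next anticancer intervention.

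Three further readings are not supported:

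- A reader might infer that medians for these endpoints will be misreported. Kaplan-Meier medians are specified only for overall survival (SAP 4.4).
- A reader might infer that a survival difference between arms would by itself separate the Kaplan-Meier curves. Under independent risks it does not: 1 − exp(−at) contains no death hazard. What would differ by arm is the amount of overstatement.
- A reader might infer that the Cox comparison is invalid. It stands as a cause-specific hazard ratio.

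Next intervention and opioid use are exploratory, first chemotherapy is not a listed objective, and the primary immune endpoint is untouched.

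**What to change.** In SAP 4.6.9, and for Figures 11 and 12:

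1. State that death without the event is a competing event for all three endpoints.
2. Report Aalen-Johansen cumulative incidence by arm, with 95% confidence intervals at the landmark times.
3. Give the number of event-free deaths by arm for each endpoint.
4. Keep the Cox model and label its hazard ratio cause-specific.

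The data are already collected, so the cost is a few sentences of SAP text and standard code. The downside is slightly more analysis and less direct comparability with Kaplan-Meier plots from earlier trials. Kaplan-Meier can be kept as a supplement for that purpose.
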